4.4 Robustness

To ensure that our estimates are robust, we commit to the following additional checks. Specifically, we will re-run the above analyses

1. Excluding all covariates

2. Using randomization inference

15 Final remarks

We commit to:

- 1• Make all data and code available after the initial publication of any academic paper or 2 years after the experiment is finished, whichever comes first.
- 2• Answer any questions pertaining to our analysis or to this document.
- 3• Make any deviations from this PAP explicit in the paper.

16 Supplementary Information

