2.2 Randomization

The 170 schools were randomly assigned to one of five treatment conditions.

1. Control 1 (No intervention) (34 schools)
2. Control 2 (No intervention) (34 schools)²
3. Treatment 1 (Random selection) (34 of schools)
4. Treatment 2 (Indegree centrality) (34 of schools)
5. Treatment 3 (Betweenness centrality) (34 of schools)

To leverage pre-treatment covariate data on the schools, we relied on an algorithmic block-randomization procedure proposed by Ryan Moore [\(2016\)](#). Specifically, we blocked on the province (Choma), the school type (Primary), urbanization (Rural) and whether a JIC was implemented before. All variables should, in theory, predict whether the JIC leads to positive outcomes pertaining to STIs. In particular, we would expect schools in Livingstone (an urban center), secondary schools, urbanized schools and those that have not seen a JIC implemented before to have the greatest potential to improve knowledge and self-reported behavior as a result of the JIC. The precise code for the blocking is attached to this application in the Supplementary Information. In Table 2, we report the resulting balance across treatment statuses. The table shows that our block randomization scheme produced very good balance across the treatment statuses for observable pre-treatment covariates.

²We included two random control groups so that one could be dropped in case a possible funding crunch. Indeed, during the baseline, some schools in Control 2 were dropped due to a funding shortage. While we were informed by the survey group that there was no precise selection criterion for dropping the schools, we will nonetheless exclude the schools in select robustness tests.

Table 2: Balance across treatment conditions

	Random		Indegree centrality		Betweenness centrality		Control 1		Control 2	
	Mean	SD	Mean	SD	Mean	SD	Mean	SD	Mean	SD
School characteristics										
Students	66	50	94	55	78	53	71	52	86	76
Choma	71	46	71	46	74	45	76	43	76	43
Primary	88	33	88	33	88	33	88	33	88	33
Rural	59	50	59	50	59	50	62	49	62	49
JIC before	3	17	3	17	3	17	3	17	6	24
Funding										
GRZ	78	42	82	39	80	41	77	42	83	38
Community	0	0	6	24	3	18	3	18	3	18
Private	16	37	12	33	17	38	13	34	3	18
Grant	6	25	0	0	0	0	6	25	10	30
Location										
Lat	-16	6	-17	1	-17	1	-17	0	-17	0
Lon	27	1	27	1	27	1	27	1	27	1
Facilities										
Nearest DEBS (km)	41	39	37	38	31	30	36	35	37	34
Lat nearest YFC	-17	0	-17	0	-17	0	-17	0	-17	0
Lon nearest YFC	27	1	27	1	27	0	27	0	27	0

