3.1 Baseline

The baseline data collection, conducted by a team of 10 trained enumerators divided into 3 groups, lasted about two months from March 16, 2017 to April 11, 2017 and from May 24, 2017 to July 11, 2017 for a total of 52 days. Data collection had to be interrupted during the month of April due to a month-long school break. The survey instrument is attached to this document. The prime reason for the baseline survey—in addition to collecting outcomes before the intervention takes place—was to map the entire friendship network in a given grade (more below).

Once data collection started, the survey team found additional ineligible schools that were either unreachable by car, did not have the targeted grades or were closed. Overall, the survey team managed to conduct a baseline in 98 out of the 102 schools in the treatment group (96% of the target), 28 out of 34 schools in the control 1 category, and 7 out of 34 in control 2. The final sample, thus, consists of 133 schools for the baseline survey. 37 of the schools are in Livingstone and 96 schools in Choma. 19 schools are secondary schools and 114 are primary schools. All students in either grade 6 (if primary school) or grade 11 (if lower secondary school) present on the day of baseline were interviewed for a total of 8,276 students.

Since some instruments are sensitive in nature (more below), we opted to administer self-administered surveys on tablet computers supported by ACASI (audio-assisted computerized assisted self-interview software) technology. Specifically, the survey was loaded unto the tablets and each question was accompanied by an audio file that read out loud the question in the desired language (options were Tonga and English). Students were given headphones for increased privacy. After hearing the question, students were to tap on the relevant answer. Finding the correct answer was facilitated by a) maximizing the number of questions with a vignette or picture or color coded, and by

b) positioning the answers on the left, middle, or right panel of the tablet and have the audio file explain where to find the answer. Two enumerators were present to help and assist in case of confusion or any other problem.

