We compare the effectiveness of targeting strategies on the total, spillover, and direct effect at the school level by estimating models analogous to equation (2) without covariate controls on the appropriately restricted samples. We note that since the subsamples of treated (or untreated) individuals in the three targeting arms are not comparable, un-adjusted comparisons warrant a causal interpretation only at the group level, and require covariate control (analogous to equation 2) to be interpreted as averages of individual effects.

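### The no-covariate robustness check drops the four blocking variables, although school loss has unbalanced school type between treated and control schools

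*SAP*

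**What the plan says.** Section 2.2 of the SAP states that "The 170 schools were randomly assigned to one of five treatment conditions", with 34 schools per arm, and that "we blocked on the province (Choma), the school type (Primary), urbanization (Rural) and whether a JIC was implemented before". The code in section 6.1 forms blocks for five arms, which gives 34 blocks of five schools. Table 2 shows the same share of primary schools in all five arms.

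Section 3.1 reports the schools surveyed at baseline: "98 out of the 102 schools in the treatment group (96% of the target), 28 out of 34 schools in the control 1 category". Control 2 kept only 7 of its 34. The section also gives 19 secondary and 114 primary schools among the 133 retained.

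Equation (1) in section 4.1 includes a covariate vector, and footnote 3 lists all four blocking variables in it, along with the student's grade. Equation (2) in section 4.2 carries the same vector. Section 4.3 compares targeting strategies on the total, spillover and direct effects "without covariate controls on the appropriately restricted samples". Section 4.4 then commits to two re-runs of the analyses: "Excluding all covariates" and "Using randomization inference". Neither item mentions the blocks.

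Footnote 2 says that some Control 2 schools were dropped for lack of funds, and promises to leave those schools out in some robustness tests. It does not say which tests.

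**The concern.** An unadjusted re-run is a fair check on an adjusted model as long as the design still balances the arms. Blocking gave that balance on school type at randomisation. School loss then removed it between treated and control schools, and the first check discards the variables that would restore it.

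School type matters here. Primary schools contribute grade 6 and secondary schools grade 11, and the index covers sexual-health knowledge, sexual behaviour and HIV testing. Section 2.2 itself expects the blocking variables to bear on outcomes. If grade 11 scores higher, the unadjusted contrast is pulled against the JIC; if lower, in its favour. The check could then disagree with the main model only because a known imbalance was let back in, and a reader could take that as fragility of the main result.

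Randomisation inference is justified by repeating the assignment actually used. The plan does not say that it will permute within blocks.

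**Working it through.** **The plan's own figures.** 98 + 28 + 7 = 133 schools; 98/102 = 96.1%, stated as 96%; 19 + 114 = 133. All agree.

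**School type at randomisation.** Table 2 reads "Primary 88 33 88 33 88 33 88 33 88 33" (mean and SD for each arm). The only count out of 34 that rounds to 88% is 30, so each arm had 30 primary and 4 secondary schools: 150 and 20 in total, or 4/34 = 11.8% secondary in every arm.

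**Who was lost.** 20 - 19 = 1 secondary school and 150 - 114 = 36 primary schools. The single lost secondary school came from the treated arms, Control 1 or Control 2, which leaves three cases:

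| Secondary retained (treated, C1, C2) | Treated, of 98 | Pooled control, of 35 | Treated minus pooled control | Treated minus C1 alone |
|---|---|---|---|---|
| 11, 4, 4 | 11.2% | 8/35 = 22.9% | -11.6 points | -3.1 points |
| 12, 3, 4 | 12.2% | 7/35 = 20.0% | -7.8 points | +1.5 points |
| 12, 4, 3 | 12.2% | 7/35 = 20.0% | -7.8 points | -2.0 points |

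Control 2 drives the result: of its 7 retained schools, 3 or 4 are secondary (42.9-57.1%). Its retention was 3-4 of 4 secondary schools but only 3-4 of 30 primary schools.

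**Shift in the unadjusted contrast.** With schools weighted equally, shift = (difference in secondary share) x (outcome gap between secondary and primary schools). The gap is not in the document, so a range is assumed:

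- 0.25 SD: 0.078 x 0.25 to 0.116 x 0.25 = 0.02 to 0.03 SD
- 0.5 SD: 0.04 to 0.06 SD
- 1.0 SD: 0.08 to 0.12 SD

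These figures pool the three strategies. H1 is estimated strategy by strategy. Four treated schools were lost in all, so each strategy keeps 30 to 34. The smallest gap in secondary share is 20.0% - 4/30 = 6.7 points, and the largest is 22.9% - 3/33 = 13.8 points.

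**Other contrasts.** For province, the counts allow a treated-minus-control difference in the Livingstone share anywhere from -8.8 to +6.7 points, so nothing can be concluded. Between the treated arms, 4 of 102 schools were lost, so at least 30 of the 34 blocks keep all three strategies. The secondary share can differ between two treated arms by at most 3.8 points (4/31 - 3/33).

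**The case against.** The strongest reply is that the plan already adjusts where it counts. Equation (1) contains all four blocking variables and the student's grade. Blocks were formed from those four two-category variables alone, so separate indicators for blocks that share the same values would correct no further imbalance on them. This stands. A reader might infer that the main H1 estimates are biased because no model has block terms; the documents do not support that. A changed allocation ratio biases the estimate only if blocks still predict outcome after these covariates, and nothing in the SAP shows that they do.

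A reader might also infer that the strategy comparisons are confounded by school loss. The H2 comparison keeps the covariates. Only the section 4.3 network comparisons drop them, and these set treated arms against each other, where loss was slight. Section 4.3 also limits its unadjusted comparisons to a group-level reading.

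Footnote 2 is a partial safeguard, since against Control 1 alone the imbalance nearly vanishes. But it is not tied to the no-covariate check, which as written would use whatever control sample the main analysis uses.

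On randomisation inference, the plan nowhere proposes free permutation, and the blocking code and seeds are printed. What is missing is one clarifying clause.

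Finally, full block indicators would be expensive. Each per-strategy model has about 65 to 69 schools (30 to 34 treated plus 35 control), and up to 33 indicators would absorb about half of the school-level information. They are not needed.

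**Conclusion.** The point holds for the treated-versus-control contrasts in the first robustness check, and it is minor. The plan's own counts force a treated-minus-control difference in secondary share of -7.8 to -11.6 percentage points, against zero at randomisation, and the check removes the variable that would correct for it. The resulting shift is about 0.02 to 0.12 SD for assumed grade gaps of 0.25 to 1 SD.

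Three assumptions lie behind this. School type was classified in the same way in Table 2 and in the baseline counts. The grade gap is unknown, hence the range. Schools are weighted equally, whereas equation (1) is fitted to students; the student-weighted imbalance depends on grade sizes by school type and arm, which the SAP does not give.

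The primary H1 estimate and the H2 comparison are largely protected by their covariates. For randomisation inference, the finding is only that its link to the blocks is unstated.

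**What to change.** In section 4.4, redefine the first check as excluding all covariates except the four blocking variables, or indicators for their observed combinations. If a fully unadjusted run is still wanted, report it beside this version and note the imbalance in school type.

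State that randomisation inference re-randomises within the blocks produced by the code in section 6.1, and how blocks with lost schools are handled.

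Keeping the same terms in the section 4.3 network-estimand comparisons is optional. The reason there would be precision and consistency with the design, not removal of material bias.

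The cost is SAP wording and a few degrees of freedom: four if the variables enter additively, somewhat more with indicators for their combinations. No new data are needed.

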6.1 Blocking code

```
rm(list = ls())
setwd("")

data <- read.csv("population_cleaned.csv")
data$id <- seq(1:length(data[,1]))
set.seed(52273)
library(blockTools)

data$groups = 1
data$nearest_yfc <- ifelse(is.na(data$geolat$yfc), 1, 0)

out <- block(data,
              groups = "groups",
              n.tr = 5,
              id.vars = c("id"),
              block.vars = c("choma_vs_livingston", "primary_vs_secondary", "rural_vs_urban", "jic_implemented_before"), #we only block on non
              #dist_debs_km", "dist_yfc_km", "dist_hf_km"),
              #grz", "community", "private", "grant", "geo_lat", "geolat",
              #male_pupil", "female_pupil", "pre_test"),
              algorithm = "optGreedy",
              distance = "mahalanobis",
              level.two=FALSE,
              verbose=TRUE)

assg <- assignment(out, seed = 5212)
outCSV(out)
```

```

treatments<- read.csv("Group1.csv")
treatment1<- cbind(treatments[2], "random")
colnames(treatment1)<- c("Unit", "Treatment")
treatment2<- cbind(treatments[3], "change-maker")
colnames(treatment2)<- c("Unit", "Treatment")
treatment3<- cbind(treatments[4], "change-maker-friends")
colnames(treatment3)<- c("Unit", "Treatment")
treatment4<- cbind(treatments[5], "control1")
colnames(treatment4)<- c("Unit", "Treatment")
treatment5<- cbind(treatments[6], "control2")
colnames(treatment5)<- c("Unit", "Treatment")
treatment<- rbind(treatment1, treatment2, treatment3, treatment4, treatment5)
treatment <- treatment[order(treatment$Unit),]
treatment <- as.matrix(treatment[2])
data<- data[order (data$id),]
data$treatment <- treatment
table(data$treatment)

data$treatment~change-maker<-c(ifelse(data$treatment=="change-maker",1,0))
data$treatment~change-maker-friends<-c(ifelse(data$treatment=="change-maker-friends",1,0))
data$treatment~random<-c(ifelse(data$treatment=="random",1,0))
data$treatment~control1 <-c(ifelse(data$treatment=="control1",1,0))
data$treatment~control2 <-c(ifelse(data$treatment=="control2",1,0))

#write.csv(data, "randomization.csv")

```

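### The allocation code as printed never uses its own seeded draw, so it does not by itself support the random assignment stated in section 2.2

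*SAP*

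**What the plan says.** SAP section 2.2 states: "The 170 schools were randomly assigned to one of five treatment conditions". Each arm has 34 schools, formed after blocking on province, school type, urbanisation and earlier exposure to the JIC. The section continues: "The precise code for the blocking is attached to this application in the Supplementary Information".

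The listing in section 6.1 runs in this order:

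1. It sets a seed, "set.seed(52273", and calls `block()` with five units per block. The result is stored as `out`.
2. It draws an assignment with a second seed: "assg <- assignment(out, seed = 5212".
3. It exports with `outCSV(out)`.
4. It reads a file back, "treatments<- read.csv('Group1.csv", and names the columns in sequence, from "treatment1<- cbind(treatments[2], 'random" to "treatment5<- cbind(treatments[6], 'control2".
5. It builds the treatment variable from these labels. The final line, which would save the result, is commented out.

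Section 4.4 plans randomisation inference as one of two robustness checks and does not say how the re-draws are made.

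**The concern.** A seeded draw that nothing later refers to cannot determine which arm a school enters. On the route shown, a school's arm depends only on its position within its row of the block file. The allocation is then random only to the extent that this position is random, and the document is silent on that.

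Two things are at stake. Every arm comparison takes its causal reading from random assignment. Randomisation inference also needs the mechanism that actually produced the arms, because its p-values come from re-drawing under that mechanism.

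**Working it through.** **1. The plan's own figures.** Section 2.2 gives 170 schools and five arms: 170 / 5 = 34 per arm, which reproduces. With five units per block, there are also 34 blocks.

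**2. Trace of the listing.** `assignment(out, …)` stores its result under the new name `assg` and leaves `out` unchanged. `assg` occurs once. The only export call takes `out`. With `out` given, every value of seed 5212 therefore yields the same labels. Had `assg` been exported, each block could take 5! = 120 orders, giving 120^34 ≈ 4.9 × 10^70 possible allocations.

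**3. Can the blocking variables fix the order within a block?** Table 1 reports all four as percentages, and their SDs are those of yes/no variables. For example, Choma is 125/170 = 0.735, and √(0.735 × 0.265 × 170/169) = 0.442, against the printed 44.2. Four such variables give at most 2^4 = 16 profiles for 170 schools, or more than ten schools per profile on average. Many schools must tie exactly. Their order then depends on how ties are handled, which could be random or could follow row order in the input file. The document does not say which.

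**4. Would covariate adjustment protect the main model?** Footnote 3 to section 4.1 includes all four blocking variables. Table 2 shows how little they differ between arms (per cent):

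| Variable | Random | Indegree | Betweenness | Control 1 | Control 2 |
|---|---|---|---|---|---|
| Choma | 71 | 71 | 74 | 76 | 76 |
| Primary | 88 | 88 | 88 | 88 | 88 |
| Rural | 59 | 59 | 59 | 62 | 62 |
| JIC before | 3 | 3 | 3 | 3 | 6 |

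Blocking has already nearly balanced these variables, so adjusting for them does little about a non-random order within blocks. If that order followed unmeasured school traits, the adjusted models and the unadjusted ones (sections 4.3 and 4.4) would be affected much alike.

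**5. Can a file comparison tell the sources apart?** These figures describe the check, not the size of the problem. Between a fixed order and an independent within-block draw, expected agreement per block is:

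- five arm labels: 5 × 1/5 = 1.0 (variance 1.00)
- two controls merged: 3 × 1/5 + 2 × 2/5 = 1.4 (variance 1.14)
- JIC against no JIC: 3 × 3/5 + 2 × 2/5 = 2.6 (variance 1.44)

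Over 34 blocks this gives 34.0 (SD √34 = 5.8), 47.6 (SD 6.2) and 88.4 (SD 7.0) of 170. In 100,000 simulated draws with five labels the maximum was 67. A faithfully reproduced true source agrees on 170.

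Section 3.1 reports: "The final sample, thus, consists of 133 schools for the baseline survey" (98 + 28 + 7). If the fielded arm can be confirmed only for these schools, chance agreement is 133 / 5 = 26.6 (SD 5.0 by simulation, taking schools as missing at random within arm). All five labels should be used, since merging arms weakens the contrast.

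**The case against.** The strongest reply is that the document shows an unused object in an appendix and nothing about the real allocation. Much of this stands:

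- Section 2.2 presents the listing as code for the blocking, not for the assignment.
- A seed is set before `block()`, so that function may randomise order itself.
- The text was read from PDF. Some tokens are not valid code, and the listing breaks between the export and the line that reads the file, so a lost line cannot be excluded.
- The save line is commented out, so nothing ties this script to the fielded list.

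What does not stand is that the listing concerns blocking alone. It goes on to build and tabulate the five-arm treatment variable, and it is the only route from school to arm that the document shows.

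Three stronger readings are tempting and not supported:

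- *The schools were not randomised.* This would require knowing that the order of `out` is non-random and was fielded. The document shows neither.
- *Table 2 proves labelling by position.* Choma, Rural and JIC before all rise or stay level across the columns in the code's order. Only 2 of 120 orders of whole columns would show this, or 4 of 120 in either direction. But the pattern was noticed after the fact, it rests on differences of one or two schools, and shuffling whole columns is not the within-block design.
- *Only the unadjusted analyses and randomisation inference are exposed, because the main model adjusts for the blocking variables.* Step 4 of the working shows why that adjustment gives little protection.

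**Conclusion.** The point holds as a defect in the record of the allocation. As printed, the only assignment route shown discards its random draw. It supports the statement in section 2.2 only if `block()` randomises order within blocks or if a different script was fielded.

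No bias is shown, and its size cannot be computed from the document. The conclusion assumes that the listing is complete at the point of export. If `assg` was in fact fielded, only the listing is wrong and the analyses stand. If a non-random order of `out` was fielded, all arm comparisons, adjusted or not, rest on an as-if-random assumption, and within-block re-draws are not a valid reference set.

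This should be fixed. Confidence is high for the reading of the printed listing and does not extend to what happened in the field.

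**What to change.** Before endline outcomes are analysed (section 3.4 schedules endline for October 2017), compare the fielded list of 170 schools, on all five arm labels, in two steps. First compare it with the archived Group1.csv. Then compare it with re-runs of `out` and `assg`, using the archived input file in its original row order, both seeds and the original software versions. The references give only the package version, 0.6-3. Treat a mismatch on re-running as possibly a failure to reproduce, not as proof of another source.

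- **If `assg` was fielded:** correct the listing to export `assg`, and base randomisation inference on re-draws within the 34 blocks of five.
- **If the column order of `out` was fielded:** disclose this in section 2.2. Unless `block()` is shown to randomise that order, do not present within-block re-draws as design-based inference, and state that all arm comparisons, adjusted and unadjusted, rest on an as-if-random assumption.
- **If neither matches:** state the actual source.

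The cost is a file comparison, the re-runs, and a corrected listing or a short disclosure. Schools and fieldwork are unchanged. The downside is a possibly less favourable description of the allocation and the possible loss of one of the two robustness checks.
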